### **9.3 Primary Endpoint Analysis**

The primary endpoint analysis will be a time to event analysis and account for censored observations for all randomized subjects. Intention to treat analysis will be used for this endpoint; the analysis will be “analyzed as randomized” regardless of the actual treatment patients receive during the follow-up period. Kaplan-Meier (1958) estimates of the primary endpoint and overall survival will be generated along with 95% confidence intervals for the median time to event or death (Brookmeyer and Crowley, 1982).(8,9) Log-rank test will be used to compare the hazard functions between the two groups. Cox (1972) regression models will be fit to assess and adjust for baseline covariates.(10) The median time to VT recurrence as well as the 95% confidence intervals will be reported for both groups. The event free survival probability as well as the 95% confidence intervals at the 24-month follow-up for both groups will be presented. Adverse events will be tabulated by type and level of severity and compared between groups using chi-square or Fisher exact tests.

Secondary analyses comparing outcomes in the ICD+ablation and ICD arms vs. the registry patients (ablation only) will be performed in a similar manner to those described above.

Interim analyses will be generated by the coordinating center annually. A Peto-Haybittle efficacy monitoring boundary will be used: if the p-value for the difference between groups is <0.001, early stopping of the trial will be considered. Using this monitoring bound, the p-value for statistical significance at the final analysis will remain at the nominal 0.05 level.

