### **3. STUDY DESIGN**

#### **3.1 Study Objective**

The study is a prospective, multi-center, randomized controlled trial evaluating the efficacy of ICD plus catheter ablation vs. ICD alone in preventing recurrent VT, cardiovascular rehospitalization, and death in patients with primary and secondary indications for ICD implantation.

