### 3.4.1 Inclusion Criteria

- Patient is receiving a new ICD or CRT-D implant that has study required programming capabilities and is appropriate for remote monitoring. Patient who has received the ICD / CRT-D within 90 days of enrollment can also be enrolled.
- Patient who has a high risk of ICD shock as shown by documented Monomorphic VT (MMVT) by one or more of the following:
  - Spontaneous MMVT
  - Inducible MMVT during EP Study,
  - Inducible MMVT during NIPS Study

\*Inducible MMVT is defined as MMVT > 30 seconds or requiring electrical termination (ATP or cardioversion)

- Patient has EF < 50% or RV dysfunction
- Patient has a cardiomyopathy with structural heart disease of any cause
- 18 years of age or older
- Patient has been informed of the nature of the study and has agreed to its provisions and provided written informed consent approved by the Institutional Review Board.

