#### **3.5.1 Randomization**

Subjects who meet inclusion/exclusion criteria will be entered into the randomized trial. Randomization will be 1:1 between control group and ablation group. Those randomized to the control group will receive ICD therapy and routine drug therapy (including antiarrhythmic drugs as indicated). Subjects randomized to the ablation group will receive ablation therapy plus ICD for ventricular tachycardia. Patients that refuse ICD therapy and undergo ablation only will be enrolled in a prospective registry. All primary statistical analyses will be performed on an intent-to-treat basis.

Central randomization is conducted by the coordinating site. Prior to 10/12/16, the participating sites performed randomization using a table (block size of 4) provided by the coordinating site. After additional in-house statistical review of the protocol, electronic randomization from the coordinating site was advised. Central electronic randomization commenced on 10/12/2016. 25 patients were enrolled using the original randomization table schema. The remaining patients were randomized using electronic randomization.

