## **9. STATISTICAL ANALYSIS**

### **9.1 Sample size and power calculation**

Based on assumptions from the SMASH VT trial and the AVID study, a 50% reduction in events from ablation is projected with a 50% event rate in the control arm at 2 years. 120 patients are required to achieve 80% power to detect a true difference of this magnitude with a two-sided alpha error of 0.05. The primary endpoint is a composite that includes cardiovascular rehospitalization and death, which will increase event rates at an estimated 10%/year, individually.

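### The primary log-rank could be stratified by qualifying arrhythmia (any spontaneous MMVT vs inducible only): a cheap improvement whose gain in power depends on case mix and prognostic strength the documents do not give

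*Combined protocol and SAP*

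**What the plan says.** - **Primary test.** Section 9.3: "Log-rank test will be used to compare the hazard functions between the two groups". No strata are named. The same paragraph says that Cox "regression models will be fit to assess and adjust for baseline covariates". It lists no covariates and does not say whether the Cox result is primary or supportive.
- **Randomization.** Section 3.5.1: "Randomization will be 1:1 between control group and ablation group". The first 25 patients were allocated from site-held tables in blocks of 4, the rest by central electronic randomization. No stratification factor is named for either phase.
- **Population.** Section 3.4.1 accepts one or more of three routes: spontaneous monomorphic VT (MMVT), "Inducible MMVT during EP Study", or MMVT induced at a NIPS study. Section 3.1 adds that the trial covers "patients with primary and secondary indications for ICD implantation".
- **Data.** Section 4.8 lists the selection criteria among the components of the case report form. It describes no separate field for the qualifying route.
- **Planned size.** Section 9.1: "a 50% reduction in events from ablation is projected with a 50% event rate in the control arm at 2 years", and "120 patients are required to achieve 80% power" at a "two-sided alpha error of 0.05".

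The documents give neither the expected split between spontaneous and inducible-only patients nor event rates by route.

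**The concern.** Recurrent VT is a component of the primary endpoint (Section 9.2). Whether a patient has already had VT spontaneously is therefore a natural candidate prognostic factor. Nothing described in the randomization balances it between arms, and the log-rank does not use it.

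Two things are at stake. If the factor is prognostic, a test that leaves it out loses some power, in a trial sized with little to spare. And with 60 patients per arm, a chance imbalance on a prognostic factor moves an unstratified result in one direction or the other. A stratified test compares like with like and largely removes that dependence.

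**Working it through.** **Inputs from the documents.** Control risk 50% at 2 years and a 50% reduction, so 25% with ablation; 60 per arm; two-sided alpha 0.05; 2-year follow-up (Sections 3.5.1, 9.1, 9.2). **Assumptions.** Exponential times, the same treatment hazard ratio (HR) in both strata, no dropout. Also assumed are the spontaneous share (50, 75 or 90%) and R, the hazard ratio of the higher-risk route (taken as spontaneous) against the other (1 to 4).

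**Step 1: reproduce the plan's sample size.**
- HR = ln(0.75)/ln(0.50) = 0.415.
- Freedman events = (1.960 + 0.842)² × [(1 + 0.415)/(1 - 0.415)]² = 7.85 × 5.85 = 45.9, so 46.
- Mean event risk = (0.50 + 0.25)/2 = 0.375, so N = 46/0.375 = 123, close to 120.
- The two-proportion power at 60 per arm is 81.6%. The plan's figure reproduces.

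**Step 2: chance imbalance.** For a factor present in half the patients, the SD of the between-arm difference in its proportion is √(2 × 0.25/60) = 0.091, or about 9 points. This assumes allocation that is unrestricted with respect to the factor.

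**Step 3: average power.** 120 patients were simulated in blocks of 4, with overall control risk held at 50% and the treatment HR at 0.415 within each stratum. There were 6,000 trials per cell, and 40,000 for R = 1, 1.5 and 2 at the 50% and 75% shares. Entries are stratified minus unstratified power, in percentage points:

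| R | 50% spontaneous | 75% | 90% |
|---|---|---|---|
| 1 | -0.4 | -0.5 | -0.2 |
| 1.5 | +0.2 | +0.2 | -0.3 |
| 2 | +1.4 | +0.9 | +0.4 |
| 3 | +4.5 | +2.2 | +1.0 |
| 4 | +7.3 | +2.9 | +1.2 |

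For example, at R = 2 and a 50% share, power is 80.8% unstratified and 82.2% stratified. The standard error of a single power figure at 6,000 trials is √(0.82 × 0.18/6000) = 0.5 points, so the smallest entries are close to noise. Type I error was 4.7 to 5.2% for both tests.

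Holding the overall risks at 50% and 25% instead, at a 50% share, gives 82.3% vs 81.8% (R = 1), 82.7% vs 84.2% (R = 2), 82.9% vs 86.7% (R = 3) and 83.3% vs 89.6% (R = 4).

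If the 50% reduction is read as HR 0.50, unstratified power is only about 66% at R = 1, and stratifying changes power by about -1 to +9 points over the grid.

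**Step 4: power given an imbalance.** Take 33 of 60 higher-risk patients in the ablation arm and 27 of 60 in control, with overall risks of 50% and 25%. An adverse imbalance at least this large occurs in about 1 trial in 6. At R = 2, power is about 77% unstratified and 84% stratified. With the opposite imbalance (27 vs 33), it is about 88% and 84%. The stratified test barely moves; the unstratified one swings by about 11 points.

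**The case against.** The strongest reply is that an unstratified log-rank is valid here, that Section 9.3 already provides for covariate adjustment, and that the rest is preference. Much of this stands.

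- Type I error is about 5% either way, so this is a matter of efficiency and robustness, not of validity.
- The gain is conditional. Section 3.4.1 puts all three routes under one high-risk criterion and does not rank them. An R of 4 at an even split implies control risks of about 28% and 72%, which nothing in the documents supports.
- Part of the gain when overall risks are held at 50% and 25% comes from a stronger within-stratum effect: the HR goes from 0.415 at R = 1 to 0.378 at R = 4. In that set-up unstratified power does not fall as R rises.
- The routes can overlap, so a hierarchy has to be defined.

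A reader might go further and infer that stratifying gains power at no cost. The table contradicts this: a non-prognostic factor costs up to about half a point. A reader might also infer that randomization was simple throughout, or that Cox adjustment is demoted to a secondary role. Section 3.5.1 describes blocks of 4 for the first 25 patients, and Section 9.3 places the Cox models beside the log-rank without ranking them. Nor is the mix of primary and secondary ICD indications in Section 3.1 the same classification as spontaneous vs inducible only.

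What does not stand is that the Cox sentence settles the matter. It names no covariate and gives the model no role, so it leaves the primary p-value unadjusted.

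**Conclusion.** The point holds as a cheap improvement. The primary log-rank leaves out a baseline factor that should be derivable from recorded entry criteria and that nothing in the described randomization balances.

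At the planned 50% vs 25%, stratifying changes power by about -0.5 points if the factor is not prognostic, about 0 to +2 points at a factor HR of 1.5 to 2, and about +1 to +7 points at 3 to 4. The upper end needs a strong factor and a near-even split. For a moderate factor, the better argument is protection against an unlucky allocation: about 77% vs 84% power in the 33 vs 27 example.

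These sizes rest on assumed prognostic strength and case mix, proportional hazards, a common treatment effect across routes and no dropout. They do not show that the planned test is wrong or that the trial is underpowered because of it.

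**What to change.** In Section 9.3:
1. Define two strata from the baseline selection criteria: any spontaneous MMVT, and inducible only (at EP or NIPS study). A patient with both goes in the first.
2. Make the primary test a two-sided log-rank stratified on this factor, and take the HR and its 95% confidence interval from a Cox model stratified the same way, with treatment as the only covariate. Test and estimate then rest on the same model. Further adjustment, for example for LVEF, was not evaluated here and is not part of this change.
3. Keep the unstratified log-rank as a sensitivity analysis.
4. Fix the change, with a dated record, before anyone sees outcomes by arm. Database lock is too late as a safeguard, because Section 9.3 plans annual interim analyses by the coordinating center. Section 1 (Length of Study) states that no analysis had been done as of 28 April 2020, so there was room for this at that date. Use the same stratified test at any interim look.

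Cost: SAP wording, derivation of one baseline variable, and up to about half a point of power if the factor turns out not to be prognostic. No new patients or assessments should be needed.

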### **3.6.3 Discontinued Subjects**

- Lost to follow-up: subjects may be lost to follow-up despite exhaustive attempts to contact them. A minimum of two (2) attempts (by telephone or mail) to contact such subjects will be made and then a certified letter will be sent to the last known address. Attempts to contact the subject will be documented.
- Subject/Family request: subjects may voluntarily decide to withdraw from the study with no penalty. If a subject chooses to discontinue participation in the study at the time of a study visit, the required assessments for that visit will be completed. If the subject notifies the clinical center by mail or phone, he/she may be requested to come in to have a final assessment.
- Subject's participation terminated by Investigator: a subject's participation may be discontinued if the Investigator considers that it is in the subject's best interest.
- Subject's participation terminated by site PI request.
- Subject Death.

If a patient is discontinued from the study, the reason for discontinuation will be documented and the data collected from this subject will be used in the final analysis and treated as censored subject.

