### **9.2 Primary Endpoint**

The primary efficacy endpoint is defined as freedom from recurrent VT, cardiovascular rehospitalization, and all-cause mortality through a period of 2 years after the procedure (ablation) or randomization (standard medical therapy). Recurrent VT is defined as any appropriate ICD therapy (shock or ATP) or documented sustained monomorphic VT >30 seconds. Cardiovascular rehospitalization is defined as a hospital admission after the randomized procedure for heart failure, procedure-associated complication, or arrhythmia-related causes during the follow-up period.

Prespecified secondary endpoints include each of the individual components of the primary endpoint. Comparison of the ablation-only registry with the randomized patients will serve as an additional secondary outcome measure.

Prespecified subgroup analysis will be performed for patients with RV cardiomyopathy.

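### VT recurrence alone is to be summarised by a median that the ablation arm is unlikely to reach, and no method treats death as a competing event for the component endpoints

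*Combined protocol and SAP*

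**What the plan says.** Section 9.2 defines the primary endpoint as a composite of recurrent VT, cardiovascular rehospitalization and all-cause death over 2 years, and adds: "Prespecified secondary endpoints include each of the individual components of the primary endpoint". VT recurrence and rehospitalization will therefore each be analysed alone.

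Section 9.3 assigns Kaplan-Meier curves, with Brookmeyer-Crowley intervals for the median, to the composite and to overall survival. Log-rank and Cox methods are named for comparing the arms. For VT recurrence it adds one specific commitment: "The median time to VT recurrence as well as the 95% confidence intervals will be reported for both groups". It also plans a 24-month event-free probability with 95% CI, but does not tie it to the components.

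Section 3.6.3 includes death in its list of reasons for discontinuation and says of a discontinued subject that "the data collected from this subject will be used in the final analysis and treated as censored subject".

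Neither section names a summary method for rehospitalization. Cumulative incidence, Fine-Gray and cause-specific analysis appear nowhere.

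**The concern.** A patient who dies without VT recurrence can no longer have one. Censoring such a patient treats them as still able to recur at the same rate as the survivors, so one minus Kaplan-Meier estimates the risk in a population where nobody dies. That exceeds the proportion of patients who actually have a recurrence. The same holds for rehospitalization analysed alone.

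At stake are the absolute risks reported for prespecified secondary endpoints. The size of the overstatement depends on mortality. Section 2.1 considers it plausible that ablation affects mortality, and Section 9.3 extends the same methods to registry patients who refused an ICD, so equal mortality across the compared groups cannot be taken for granted.

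The median raises a separate problem. At the design rates, far fewer than half of the ablation arm would recur during follow-up, so the promised figure would probably not be estimable there. With no rule written down, the handling of death and the replacement summary would be chosen after the data are seen.

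**Working it through.** **Inputs.** Section 9.1: "a 50% reduction in events from ablation is projected with a 50% event rate in the control arm at 2 years", which gives 50% against 25%. Section 9.1 on death and rehospitalization: "which will increase event rates at an estimated 10%/year, individually". Section 3.5.1: 1:1 allocation, so 60 per arm. Section 9.2: horizon of 2 years. Section 4.7: last scheduled visit at 36 months.

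**The plan's own figure.** For two proportions with 60 per arm, z = (0.25 × √60 − 1.96 × √(2 × 0.375 × 0.625)) / √(0.25 + 0.1875) = (1.937 − 1.342) / 0.661 = 0.90, so power is 81.6%. This agrees with the stated 80% for 120 patients and confirms that 50% and 25% are 2-year risks.

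**Assumptions.** Hazards are constant. Death at 10% per year is taken from Section 9.1. VT-only rates are set equal to the design rates; this is an assumption, because Section 9.1 does not make clear whether the 50% is VT alone or the composite. The documents give no dropout rate, and none is applied.

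**Formulas.** With 2-year risk r and yearly death risk d, the hazards are h = −ln(1 − r)/2 and m = −ln(1 − d).
- With deaths censored: 1 − KM(t) = 1 − exp(−ht).
- Cumulative incidence: CIF(t) = h/(h + m) × [1 − exp(−(h + m)t)].

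**VT recurrence at 24 months, d = 10%, m = 0.1054.**
- Control: h = 0.3466. CIF = 0.3466/0.4519 × (1 − 0.405) = 45.6%, against 50.0%. Excess 4.4 points.
- Ablation: h = 0.1438. CIF = 0.1438/0.2492 × (1 − 0.6075) = 22.7%, against 25.0%. Excess 2.3 points.

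**Range over the death rate.**

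| Death per year | Control excess | Ablation excess |
|---|---|---|
| 5% | 2.2 points | 1.2 points |
| 10% | 4.4 points | 2.3 points |
| 15% | 6.5 points | 3.5 points |

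**If the 50% is the composite.** Subtracting death and rehospitalization at 10% per year each leaves a control VT hazard of 0.3466 − 2 × 0.1054 = 0.1359. The 24-month VT risk is then 23.8% with deaths censored and 21.6% as cumulative incidence, an excess of about 2.2 points.

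**Between-arm contrast.** With equal mortality, the risk ratio is 0.500 with deaths censored and 0.497 from the unrounded cumulative incidences; the difference is 25.0 and 23.0 points. As an illustration of unequal mortality, ablation-arm death at 5% per year gives an ablation CIF of 23.8%, hence a ratio of 23.8/45.6 = 0.52 and a difference of 21.8 points.

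**Median.** In the ablation arm, ln 2 / 0.1438 = 4.8 years, or about 58 months. The 36-month risk is 1 − exp(−3 × 0.1438) = 35.0%. With 60 patients, the binomial chance of at least 30 events is about 0.00003 by 24 months and 1.2% by 36 months. A Kaplan-Meier curve with deaths censored can reach 50% with fewer than 30 events; simulation allowing for this gives about 0.00006 and 1.5%. In control, the median falls at exactly 24 months if VT alone is 50%, and at ln 2 / 0.1359 = 5.1 years if the 50% is the composite as above.

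**The case against.** The strongest reply has four parts.

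First, Section 9.3 assigns Kaplan-Meier only to the composite and overall survival. A reader might infer that rehospitalization is also to be shown by Kaplan-Meier with a median, but the documents do not say so; its method is simply unstated. Likewise, censoring at death in the VT analysis is inferred from Section 3.6.3 and from the absence of any other rule. Both points stand. The inference about VT remains the natural one, since the only median method named is the Kaplan-Meier one.

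Second, the bias is small beside the sampling error: with 60 per arm, the 95% half-width for a single-arm risk is about 11 to 13 points. This stands. But the excess has a known direction and costs nothing to remove.

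Third, a cause-specific log-rank or Cox analysis is numerically the same as one with deaths censored, so the comparison of arms would not change. This also stands. A reader might infer that the treatment comparison is materially biased; the calculations do not support that when mortality is equal.

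Fourth, an unreached median can be reported as not reached, with an open upper limit, and a 24-month event-free probability is already planned. So it goes too far to say that the promised result cannot be delivered. However, that 24-month figure is not linked to VT recurrence and does not deal with death.

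**Conclusion.** The point holds as one about secondary reporting. Following the plan on its most natural reading gives a 24-month VT recurrence risk that is about 2 to 4 points too high at a death rate of 10% per year, and 1.2 to 6.5 points too high over 5% to 15% per year. It also commits to an ablation-arm median that is very unlikely to be reached by 24 or 36 months. These sizes rest on constant hazards and on VT rates taken from the design assumptions; they are projections.

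A reader might infer that the primary result is compromised as well. It is not, because Section 9.2 counts death as an event in the composite. Read literally, though, the censoring rule in Section 3.6.3 contradicts that definition, and the two sections should be reconciled.

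**What to change.** In Sections 9.2 and 9.3:
- For VT recurrence and cardiovascular rehospitalization analysed alone, report Aalen-Johansen cumulative incidence at 24 months by arm, with death as a competing event, and the between-arm difference with its 95% CI.
- Keep the log-rank and Cox comparison for these components and label it cause-specific.
- Make the 24-month cumulative incidence the main VT summary in place of the median, and report the median only if it is reached.
- Keep Kaplan-Meier for the composite and overall survival.

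In Section 3.6.3, state that death is an event in the composite and a competing event for the non-fatal components, and limit censoring to subjects who leave the study alive.

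The cost is SAP wording and standard software. Sections 4.8 and 5.3 already provide for a death report and the date of death, so no new data are needed.

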## 1. PROTOCOL SUMMARY

Title:	Pan-Asia United States PrEvention of Sudden Cardiac Death Catheter Ablation Trial (PAUSE-SCD)
Objective:	

1) To assess the incidence of sudden cardiac death and impact of ablation and ICD therapy vs. ICD therapy alone in Asia, which has not been studied in randomized trials except in the US and Europe.

2) To explore the impact of preemptive VT ablation alone in patients at risk for sudden death (observational registry cohort).

Sample Size:	Pilot study sample size of 120 randomized patients (60 ICD and 60 ICD+ablation). Registry is reserved for patients who refuse randomization and received ablation only.
Design:	Prospective, multi-center randomized, controlled study.
Clinical Sites:	Approximately 8-12 ablation centers in Asia (China, Korea, Japan) will participate in the study. Additional centers may be considered based on the discretion of the principal participating centers. The anticipated enrollment duration is 24 months for the initial pilot enrollment. Additional associated centers may be used for referrals, clinically indicated ICD implantation, NIPS study, and ICD follow up. Due to the COVID19 global pandemic, China centers were shut down and complete access for patient follow-up will require an additional 6-12 months. Therefore, we are requesting one extra year extension for follow up due to these unanticipated circumstances. No statistical review or analysis was performed, as follow-up remains incomplete as of April, 28 th , 2020.
Inclusion Criteria:	

• Patient is receiving a new ICD or CRT-D implant, that has study required programing capabilities and is appropriate for remote monitoring. Patient who has received the ICD / CRT-D within 90 days of enrollment can also be enrolled.

• Patient who has a high risk of ICD shock as shown by documented Monomorphic VT (MMVT) by one or more of the following:

○ Spontaneous MMVT

○ Inducible MMVT during EP Study,

○ Inducible MMVT during NIPS Study

Inducible MMVT is defined as MMVT > 30 seconds or requiring electrical termination ( ATP or cardioversion)

- Patient has EF < 50% or RV dysfunction
- Patient has a cardiomyopathy with structural heart disease of any cause
- 18 years of age or older

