## 7. EXPLANATIONS OF RISKS AND MITIGATIONS TO SUBJECTS

### 7.1 Risks

The following complications have been reported for commercially available ablation catheters or in published literature and are expected to be similar to those anticipated in this study. The list of complications includes but is not limited to:

- Death
- Cardiogenic shock
- Complete Heart Block
- New incessant VT/VF
- Acute MI
- Stroke
- Pericarditis
- Cardiac perforation causing pleural effusion or tamponade

- Adverse effects on implantable pacemakers, cardioverters, and defibrillators
- Coronary artery occlusion
- Heart Valve injury
- Acute Pulmonary edema
- Pulmonary embolism
- Vascular access complications
- Phrenic nerve injury
- Arterial/venous thrombus: Clot formation in the artery or vein.
- AV fistula: An abnormal passageway between an artery and a vein.
- Catheter insertion site hematoma
- Hemopneumothorax
- Hypoxia
- Infection: Localized or systemic
- Peripheral venous thrombosis
- Phrenic nerve damage
- Pneumonia
- Pseudoaneurysm
- Radiation injury resulting in dermatitis
- Respiratory failure
- Radiation exposure during the fluoroscopic imaging of the catheters may slightly increase the lifetime risk of developing a fatal malignancy or a genetic defect in offspring
- Fluid overload resulting in pulmonary edema and exacerbation of congestive heart failure (these risks are specific to open irrigated ablation catheters)

Additional risks related to Epicardial Ablation:

- RV puncture
- Pericardial bleeding
- Hemoperitoneum
- Coronary Artery Damage
- Phrenic Nerve Damage
- Pleural Damage
- Myocardial Infarction
- Abdominal Bleeding
- Pericarditis

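### Adverse events are compared between arms only by an unspecified choice of chi-square or Fisher test, with no risk difference or interval, and at 60 per arm those p-values say little about harm

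*Combined protocol and SAP*

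**What the plan says.** The whole adverse event analysis is one sentence in section 9.3: "Adverse events will be tabulated by type and level of severity and compared between groups using chi-square or Fisher exact tests". It gives no rule for choosing between the two tests, does not say whether the chi-square is continuity-corrected, sets no significance threshold and asks for no effect size. For efficacy the same section does plan intervals: "Kaplan-Meier (1958) estimates of the primary endpoint and overall survival will be generated along with 95% confidence intervals", and also 95% intervals for event-free survival at 24 months.

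No safety endpoint is defined. Section 7.1 lists the harms expected from ablation and introduces them with "The following complications have been reported for commercially available ablation catheters or in published literature", but gives no rates.

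Some harm is captured outside the adverse event tables. All-cause death is part of the primary composite, and overall survival gets its own Kaplan-Meier estimate. Section 9.2 also counts certain readmissions: "Cardiovascular rehospitalization is defined as a hospital admission after the randomized procedure for heart failure, procedure-associated complication, or arrhythmia-related causes". Each component of the composite is a secondary endpoint.

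**The concern.** Several harms in section 7.1, such as cardiac perforation, vascular access complications and RV puncture, arise mainly from the ablation procedure. For these the control arm will contribute few events, and the useful question is how large the excess is and how precisely it is known. A p-value for each event type does not answer that.

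The sample size was set for a large effect on a common endpoint and not for uncommon harms. At small counts a p-value is weak evidence either way. If the test is left open, it can also depend on a choice made after the counts are seen. At stake is the benefit-risk statement: a reader could be given a non-significant p-value without being told that an excess of many percentage points remains compatible with the data.

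**Working it through.** **Inputs from the documents.** 120 randomized, 60 per arm (section 1); "Randomization will be 1:1 between control group and ablation group" (section 3.5.1); two-sided alpha 0.05 and 80% power, stated for the primary endpoint only (section 9.1).

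**Assumptions.** The documents give no complication rate, so counts of 3 to 6 against 0 are illustrative. The 0.05 threshold is borrowed from the primary endpoint because none is set for adverse events.

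**Step 1: the plan's own figure.** Section 9.1 assumes "a 50% reduction in events from ablation is projected with a 50% event rate in the control arm at 2 years", that is 50% against 25%, and states "120 patients are required to achieve 80% power to detect a true difference of this magnitude with a two-sided alpha error of 0.05". With the pooled two-proportion formula, z = (√60 × 0.25 − 1.96 × √(2 × 0.375 × 0.625)) / √(0.25 + 0.1875) = (1.936 − 1.342) / 0.661 = 0.90, a power of 81.6%. The 60 per arm is reproduced. The plan gives no corresponding figure for adverse events.

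**Step 2: p-values for a events against 0, 60 per arm.**
- Fisher, two-sided: p = 2 × C(60,a) / C(120,a). For a = 5, 2 × 0.02866 = 0.057.
- Uncorrected chi-square: X² = 120a / (120 − a). For a = 5, 600/115 = 5.22, p = 0.022.
- Yates-corrected: X² = 120(a − 1)² / (a(120 − a)). For a = 5, 1920/575 = 3.34, p = 0.068.

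**Step 3: estimates for the same counts.** Newcombe's interval combines the Wilson limits of each arm. For 5/60 these are 3.61% and 18.07%; for 0/60, 0% and 6.02%. The lower limit is 8.33 − √((8.33 − 3.61)² + 6.02²) = 0.7%. The upper limit is 8.33 + (18.07 − 8.33) = 18.1%. The exact interval for the ablation arm alone is Clopper-Pearson.

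| Events | Fisher | Chi-square, uncorrected | Yates | Risk difference (Newcombe 95% CI) | Exact 95% CI, ablation arm |
|---|---|---|---|---|---|
| 3 vs 0 | 0.244 | 0.079 | 0.242 | 5.0% (−1.9% to 13.7%) | 1.0% to 13.9% |
| 4 vs 0 | 0.119 | 0.042 | 0.127 | 6.7% (−0.6% to 15.9%) | 1.8% to 16.2% |
| 5 vs 0 | 0.057 | 0.022 | 0.068 | 8.3% (0.7% to 18.1%) | 2.8% to 18.4% |
| 6 vs 0 | 0.027 | 0.012 | 0.036 | 10.0% (2.0% to 20.1%) | 3.8% to 20.5% |

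Against zero control events, Fisher needs at least 6 events to fall below 0.05 and uncorrected chi-square at least 4.

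**Step 4: chance of reaching those counts**, from P(X ≥ k) with X binomial(60, p) and no control events:

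| True ablation-arm rate | Fisher (k = 6) | Chi-square, uncorrected (k = 4) |
|---|---|---|
| 5% | 8% | 35% |
| 8.3% | 38% | 75% |
| 10% | 56% | 86% |
| 15% | 90% | 99% |

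**Step 5: would the usual convention settle the choice?** At 4 and 5 events against 0 the expected counts are 2.0 and 2.5 per arm, so the common rule (Fisher when an expected count is below 5) would select Fisher. The plan does not state that rule, and it would not remove every conflict. At 8 vs 2 (expected count 5) Fisher gives 0.095 and uncorrected chi-square 0.048; at 9 vs 2 they give 0.0535 and 0.0268.

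**The case against.** The best defence is that harm is not assessed by p-values alone, and that stands. The same sentence requires tabulation by type and severity, so 5/60 against 0/60 would be printed and an interval could be derived from it. Deaths and complication readmissions also enter time-to-event analyses. That cover is partial: a non-fatal complication managed during the index stay is not a readmission, and the composite mixes harm with efficacy.

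A reader might infer four stronger things that the documents do not support.

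- *That the permitted tests contradict each other at 4 or 5 events.* Only the uncorrected chi-square does so; the Yates version agrees with Fisher. The plan leaves the version open.
- *That p>0.05 will be reported as no difference in harm.* Section 9.3 sets no threshold for adverse events and no such reading rule. It is a risk of a test-only plan, not a stated intention.
- *That the test cannot flag a large excess.* It can: Fisher reaches p<0.05 with probability 90% at a true 15% against 0%. Power is low at more modest rates.
- *That control counts will be near zero throughout.* Controls also receive ICDs, section 5.1.1 counts events whether or not they are related to the procedure, and stroke, infection and pneumonia on the section 7.1 list can occur in either arm. Counts against zero are the extreme case.

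Requiring Fisher everywhere would not be a remedy in itself. It is the less sensitive choice (38% against 75% at a true 8.3%), and at 5 vs 0 it does not reach 0.05 although the Newcombe interval excludes zero.

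**Conclusion.** The concern holds in a limited form. Between-arm comparison of adverse events rests on an unspecified choice of test with no estimate or interval, in a section that plans intervals for efficacy. At 60 per arm, 5/60 against 0/60 could be reported with p = 0.022, 0.057 or 0.068, while the risk difference of 8.3% (0.7% to 18.1%) shows both the likely excess and how little is excluded. At a true 8.3% against 0%, Fisher reaches p<0.05 38% of the time.

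These figures rest on assumed counts, no control events and a 0.05 threshold borrowed from the primary endpoint. The missing rule for choosing a test is only a gap in detail. The absence of an effect estimate matters more, because it limits what the trial can say about harm. The primary analysis and sample size are unaffected. This is a minor point and a cheap improvement.

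**What to change.** Amend section 9.3 as follows.

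1. For each adverse event type, report the number of patients with at least one event in each arm and the between-arm risk difference with a 95% Newcombe interval, as the main safety summary.
2. Report the ablation-arm procedural complication rate with an exact (Clopper-Pearson) 95% interval, stating which events count and the denominator. Include complications during the index stay.
3. If p-values are kept, name one test in advance, including whether any chi-square is corrected. Treat it as descriptive, and state that p>0.05 is not evidence that harm is absent. The test and the interval can fall on different sides of the line, as at 5 vs 0, so the interval should carry the message.
4. Report registry ablation complications separately, and only if their capture is confirmed to be equivalent. Section 3.6.2 specifies demographics, history and follow-up of overall status, and does not state that procedural complications are recorded in the same way.

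The cost is a few sentences and some table columns. For randomized patients the data are already called for: adverse event assessment before discharge and at each visit (sections 4.6.1 and 4.7.1), and the ablation, discharge and adverse event forms (section 4.8). The small downside is that wide intervals will make the safety message look less certain.
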